				Height (cm)	XXX.X
				Weight (kg)	XXX.X

Note: Sex: M=Male, F=Female; Race: W=White, BL=Black or African American, AS=Asian, AI=American Indian or Alaska Native, PI=Native Hawaiian or Other Pacific Islander, O=Other, FSNC=French Sites Only - Not Collected

[1] L= Low (systolic blood pressure value <90 mmHg, diastolic blood pressure value <60 mmHg, heart rate <40 BEATS/MIN); H=High (systolic blood pressure value >140 mmHg, diastolic blood pressure value >80 mmHg, heart rate >100 BEATS/MIN); *=Newly notable abnormality if the patient did not meet the abnormality criteria at baseline

<DIRECTORY PATH>PROGRAM NAME Executed: DDMMYYYY hh:mm

Prog Note: Sort by Maximum Dose Level (400 mg, 500 mg, 600 mg, missing), Patient ID, Date.

Listing 16.2.6.8
 Physical Examination
 Safety Analysis Population

Maximum Dose Level: XXX mg

Patient ID	Age (yrs) / Sex / Race	Analysis Set	Visit / Exam Date Time (Day)	Assessment	Status	Abnormality Comment(s)
XXXXXX	50/M/W	Safety/ Efficacy	XXXX/ DDMMYYYY XX:XX (XX)	SKIN	Abnormal	XXXXXXXXXXXXXXXXXXXXXXXXXX
				HEAD, EYES, EARS, NOSE, THROAT ...	Normal	

Note: Sex: M=Male, F=Female; Race: W=White, BL=Black or African American, AS=Asian, AI=American Indian or Alaska Native, PI=Native Hawaiian or Other Pacific Islander, O=Other, FSNC=French Sites Only - Not Collected

<DIRECTORY PATH>PROGRAM NAME Executed: DDMMYYYYY hh:mm

Prog Note: Sort by Maximum Dose Level (400 mg, 500 mg, 600 mg, missing), Patient ID, Exam Date, Assessment. All assessments will be displayed for each patient.

Listing 16.2.6.9
 Electrocardiogram Results at Screening Visit
 Safety Analysis Population

Maximum Dose Level: XXX mg

Patient ID	Age (yrs) /	Sex/ Race	Analysis Set	Visit/ ECG Date Time (Day)	Normal Sinus Rhythm	ECG Parameter	Result	Status	Interpretation [1]	Abnormality Detail
XXXXXX	50/M/W		Safety/ Efficacy	XXXX/ DDMMYYYY Y XX:XX (XX)	Yes	Ventricular Rate (BEATS/MINUTE)			NCS	XXXXXXXXXX XXXXXXX
						PR Interval (msec)	XX	Not Done	CS	XXXXXXXXXX XXXXXXX
						QRS Duration (msec)	XXX		N	
						QT Interval (msec)		Not Done	NCS	XXXXXXXXXX XXXXXXX
						QTcF Interval (msec)	XXX		N	
						QTcB Interval (msec)	XXX		N	

Note: Sex: M=Male, F=Female; Race: W=White, BL=Black or African American, AS=Asian, AI=American Indian or Alaska Native, PI=Native Hawaiian or Other Pacific Islander, O=Other, FSNC=French Sites Only - Not Collected

[1] NCS=Not Clinically Significant, CS=Clinically Significant, N=Normal

<DIRECTORY PATH>PROGRAM NAME Executed: DDMMYYYYY hh:mm

Prog Note: Sort by Maximum Dose Level (400 mg, 500 mg, 600 mg, missing), Patient ID, ECG Date, Time.

Listing 16.2.6.10
 Female Reproductive Status and Pregnancy Test Results
 Safety Analysis Population

Patient ID	Age (yrs) / Sex/ Race	Analysis Set	Fertility Status	Method of Birth Control	Pregnancy Test					
					Visit	Test	Performed	Collection Date	Results	
XXXXXXXX X	33/ F/ W	Safety/ Efficacy	XXXXXX	XXXXXXXX	XXXXXX	Urine Pregnancy	Yes	DDDMMYY	XXXXXX	
						Serum Pregnancy	Yes	DDDMMYY	XXXXXX	
						FSH	Yes	DDDMMYY	XXX.X	
						XXXXXX	Urine Pregnancy	No	DDDMMYY	
						Serum Pregnancy	Yes	DDDMMYY	XXXXXX	
				FSH	Yes	DDDMMYY	XXX.X			
XXXXXXXX X	56/ F/ W	Safety/ Efficacy	XXXXXX	XXXXXXXX	XXXXXX	Urine Pregnancy	Yes	DDDMMYY	XXXXXX	

Note: Sex: M=Male, F=Female; Race: W=White, BL=Black or African American, AS=Asian, AI=American Indian or Alaska Native, PI=Native Hawaiian or Other Pacific Islander, O=Other, FSNC=French Sites Only - Not Collected

<DIRECTORY PATH>PROGRAM NAME Executed: DDMMYYYY hh:mm

Prog Note: Sort by Patient ID, Visit, Test.

Listing 16.2.6.11
 Food Intake Status
 Safety Analysis Population

Patient ID	Age (yrs) / Sex / Race	Analysis Set	Visit	Food Intake Date Time	Food Intake
XXXXXX	50/M/W	Safety/ Efficacy	WEEK1 D1	DDMMYYYY XX:XX	Liquid
			WEEK1 D2	DDMMYYYY XX:XX	Liquid
			XXXXX	DDMMYYYY XX:XX	Liquid
			XXXXX	DDMMYYYY XX:XX	Solid such as toast
			XXXXX	DDMMYYYY XX:XX	Not Applicable
			XXXXX	DDMMYYYY XX:XX	Solid such as toast

Note: Sex: M=Male, F=Female; Race: W=White, BL=Black or African American, AS=Asian, AI=American Indian or Alaska Native, PI=Native Hawaiian or Other Pacific Islander, O=Other, FSNC=French Sites Only - Not Collected

<DIRECTORY PATH>PROGRAM NAME Executed: DDMMYYYY hh:mm

Prog Note: Sort by Patient ID, Date.

Listing 16.2.6.12
 Brain MRI Results
 Safety Analysis Population

Patient ID	Age (yrs) / Sex / Race	Analysis Set	Visit	Allergy to MRI Macrocytic Contrast	Date of Scan	Result
XXXXXX	50/M/W	Safety/ Efficacy	SCREEN	No	DDMMYYYY	Normal
			WEEK1 D15	No	DDMMYYYY	Abnormal clinically significant
XXXXXX	56/F/W	Safety/ Efficacy	XXXXXX	No	DDMMYYYY	XXXXX
			XXXXXX	No	DDMMYYYY	XXXXX

Note: Sex: M=Male, F=Female; Race: W=White, BL=Black or African American, AS=Asian, AI=American Indian or Alaska Native, PI=Native Hawaiian or Other Pacific Islander, O=Other, FSNC=French Sites Only - Not Collected
 Only patients from French sites had this measurement.

<DIRECTORY PATH>PROGRAM NAME Executed: DDMMYYYY hh:mm

Prog Note: Sort by Patient ID, Date.

Listing 16.2.6.13
 Neurological Symptoms
 Safety Analysis Population

Patient ID	Age (yrs) / Sex / Race	Analysis Set	Visit	Headache	Nausea	Vomiting	Visual Disturbance	AE Number
XXXXXX	50/M/W	Safety/ Efficacy	XXXXXX	No	Yes	No	Yes	XXXX
XXXXXX	56/F/W	Safety/ Efficacy	XXXXXX	No	No	No	No	
			XXXXXX	Yes	Yes	Yes	No	XXXX
			XXXXXX	No	Yes	No	Yes	XXXX

Note: Sex: M=Male, F=Female; Race: W=White, BL=Black or African American, AS=Asian, AI=American Indian or Alaska Native, PI=Native Hawaiian or Other Pacific Islander, O=Other, FSNC=French Sites Only - Not Collected
 Only patients from French sites had this measurement.

<DIRECTORY PATH>PROGRAM NAME Executed: DDMMYYYY hh:mm

Prog Note: Sort by Patient ID, Visit.

Listing 16.2.6.14
 Neurological Examination
 Safety Analysis Population

Patient ID	Age (yrs) / Sex / Race	Analysis Set	Visit	Date of Assessment	Neurological Assessment	Result
XXXXXX	50/M/W	Safety/ Efficacy	XXXXXX	DDMMYYYY	Cranial Nerve 1	Normal
			XXXXXX	DDMMYYYY	XXXXXX	Abnormal, XXXXX
					XXXXXX	XXXXX
					XXXXXX	XXXXX

Note: Sex: M=Male, F=Female; Race: W=White, BL=Black or African American, AS=Asian, AI=American Indian or Alaska Native, PI=Native Hawaiian or Other Pacific Islander, O=Other, FSNC=French Sites Only - Not Collected
 Only patients from French sites had this measurement.

<DIRECTORY PATH>PROGRAM NAME Executed: DDMMYYYY hh:mm

Prog Note: Sort by Patient ID, Date.

Listing 16.2.7.1
 Plasma Concentrations of PRN1008
 Safety Analysis Population

Patient ID	Age (yrs) / Sex / Race	Visit	Sample Collected	Collection Date Time	Collection Timepoint	Sample Performed	Concentration (ng/mL)
XXXXXX	50/M/W	WEEK1 D1	Yes	DDMMYYYY XX:XX	Pre-Dose	Yes	LLOQ (<0.100)
					2 Hours Post Dose	Yes	XX.X
		WEEK1 D2	Yes	DDMMYYYY XX:XX		Yes	XX.X
		WEEK3 D15	No			No	
		...					

Note: Sex: M=Male, F=Female; Race: W=White, BL=Black or African American, AS=Asian, AI=American Indian or Alaska Native, PI=Native Hawaiian or Other Pacific Islander, O=Other, FSNC=French Sites Only - Not Collected
 LLOQ = Lower Limit of quantitation

<DIRECTORY PATH>PROGRAM NAME Executed: DDMMYYYY hh:mm

Prog Note: Sort by Patient ID, Visit.

Listing 16.2.7.2
 Percentage BTK Occupancy
 ITT Population

Patient ID	Age (yrs) / Sex / Race	Visit	Sample Collected	Collection Date Time	Collection Timepoint	Date Time of Last Dose	Time Since Last Dose (Hr)	BTK Occupancy (%)
XXXXXX	50/M/W	WEEK1 D1	Yes	DDMMYYYY XX:XX	Pre-Dose	DDMMYYYY XX:XX	X.X	XX.X

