8.2.5. Cumulative Incidents of CDA and CR at each Visit

The cumulative incidents of patients who are able to achieve CDA and CR by each visit will be summarized by maximum dose level and overall. This is a cumulative analysis compared to section 8.2.4. In addition, two-sided 80% and 95% CIs of the response rate will be provided for each maximum dose level and overall using the Exact (Clopper-Pearson) method.

The proportion of patients who are able to achieve CDA and/or CR without the need for doses of prednis(ol)one of greater than 0.5 mg/kg (CS doses from Day 1 to the day before the date of the visit) will also be summarized by maximum dose level and overall for each visit. Two-sided 80% and 95% CIs will be provided by using the Exact (Clopper-Pearson) method.

If a subject drops out, they will still accommodate to future unattended visits cumulatively, i.e. the denominator for this analysis would not diminish over time.

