Proportion of Patients who Achieved Control of Disease Activity (CDA) without Prednis(ol)one >0.5 mg/kg at Visit
Per Protocol Population

Table 14.2.2.4.3.1

Proportion of Patients who Achieved Control of Disease Activity (CDA) with Prednis(ol)one >0.5 mg/kg at Visit
 ITT Population

Visit	400 mg (N=xx)	500 mg (N=xx)	600 mg (N=xx)	Total (N=xx)
WEEK3 D15				
n (%)	xx (xx.x)	xx (xx.x)	xx (xx.x)	xx (xx.x)
80% CONFIDENCE INTERVAL	(xx.x, xx.x)	(xx.x, xx.x)	(xx.x, xx.x)	(xx.x, xx.x)
95% CONFIDENCE INTERVAL	(xx.x, xx.x)	(xx.x, xx.x)	(xx.x, xx.x)	(xx.x, xx.x)
WEEK5 D29				
n (%)	xx (xx.x)	xx (xx.x)	xx (xx.x)	xx (xx.x)
80% CONFIDENCE INTERVAL	(xx.x, xx.x)	(xx.x, xx.x)	(xx.x, xx.x)	(xx.x, xx.x)
95% CONFIDENCE INTERVAL	(xx.x, xx.x)	(xx.x, xx.x)	(xx.x, xx.x)	(xx.x, xx.x)
...				
WEEK25 D169				
n (%)	xx (xx.x)	xx (xx.x)	xx (xx.x)	xx (xx.x)
80% CONFIDENCE INTERVAL	(xx.x, xx.x)	(xx.x, xx.x)	(xx.x, xx.x)	(xx.x, xx.x)
95% CONFIDENCE INTERVAL	(xx.x, xx.x)	(xx.x, xx.x)	(xx.x, xx.x)	(xx.x, xx.x)

Note: Patients are classified into different dose levels according to the maximum dose they received during the 12 week treatment period.
 Control of disease activity (CDA) is defined as the time at which new lesions cease to form and established lesions begin to heal.
 Patients who achieved CDA at a specific visit and had no occurrence of daily prednis(ol)one >0.5 mg/kg before each visit date during the study treatment will be counted as responders.
 Two-sided 80% and 95% confidence intervals are calculated using the Exact (Clopper-Pearson) method.
 Percentages are based on the number of patients in the respective dose levels in the Analysis Population.

Source Data: Listing 16.2.4.1.5

<DIRECTORY PATH>PROGRAM NAME Executed: DMMMMYYYY hh:mm

Prog Note: For all efficacy and safety by visit summaries, add "unscheduled" visit after other visits if such data exist in the database.

Repeat above table with the other populations.

Table 14.2.2.4.3.2

Proportion of Patients who Achieved Control of Disease Activity (CDA) with Prednis(ol)one >0.5 mg/kg at Visit
mITT Population

Table 14.2.2.4.3.3

Proportion of Patients who Achieved Control of Disease Activity (CDA) with Prednis(ol)one >0.5 mg/kg at Visit
Per Protocol Population

Table 14.2.2.4.4.1
Cumulative Incidence of Patients who Achieved Control of Disease Activity (CDA) by Visit
ITT Population

Visit	400 mg (N=xx)	500 mg (N=xx)	600 mg (N=xx)	Total (N=xx)
Cumulative Responder Rate by WEEK3 D15				

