95% CONFIDENCE INTERVAL	(xx.x, xx.x)	(xx.x, xx.x)	(xx.x, xx.x)	(xx.x, xx.x)
...				
Cumulative Responder Rate by WEEK25 D169				
n (%)	xx (xx.x)	xx (xx.x)	xx (xx.x)	xx (xx.x)
80% CONFIDENCE INTERVAL	(xx.x, xx.x)	(xx.x, xx.x)	(xx.x, xx.x)	(xx.x, xx.x)
95% CONFIDENCE INTERVAL	(xx.x, xx.x)	(xx.x, xx.x)	(xx.x, xx.x)	(xx.x, xx.x)

Note: Patients are classified into different dose levels according to the maximum dose they received during the 12 week treatment period.

Control of disease activity (CDA) is defined as the time at which new lesions cease to form and established lesions begin to heal. Cumulative responder rate is used, i.e., any patient achieves the response at any study visit is counted into all the later study visits.

Unscheduled visits are not included in this summary.

Patients who ever achieved CDA and had no occurrence of daily prednis(ol)one >0.5 mg/kg before the first CDA date during the study treatment will be counted as responders.

Two-sided 80% and 95% confidence intervals are calculated using the Exact (Clopper-Pearson) method.

Percentages are based on the number of patients in the respective dose levels in the Analysis Population.

Source Data: Listing 16.2.4.1.5

<DIRECTORY PATH>PROGRAM NAME Executed: DDMMYYYY hh:mm

Repeat above table for the following:

Table 14.2.2.4.5.2

Cumulative Incidence of Patients who Achieved Control of Disease Activity (CDA) without Prednis(ol)one >0.5 mg/kg by Visit
mITT Population

Table 14.2.2.4.5.3

Cumulative Incidence of Patients who Achieved Control of Disease Activity (CDA) without Prednis(ol)one >0.5 mg/kg by Visit
Per Protocol Population

Table 14.2.2.4.6.1

Cumulative Incidence of Patients who Achieved Control of Disease Activity (CDA) with Prednis(ol)one >0.5 mg/kg by Visit
 ITT Population

Visit	400 mg (N=xx)	500 mg (N=xx)	600 mg (N=xx)	Total (N=xx)
Cumulative Responder Rate by WEEK3 D15				
n (%)	xx (xx.x)	xx (xx.x)	xx (xx.x)	xx (xx.x)
80% CONFIDENCE INTERVAL	(xx.x, xx.x)	(xx.x, xx.x)	(xx.x, xx.x)	(xx.x, xx.x)
95% CONFIDENCE INTERVAL	(xx.x, xx.x)	(xx.x, xx.x)	(xx.x, xx.x)	(xx.x, xx.x)
Cumulative Responder Rate by WEEK5 D29				
n (%)	xx (xx.x)	xx (xx.x)	xx (xx.x)	xx (xx.x)
80% CONFIDENCE INTERVAL	(xx.x, xx.x)	(xx.x, xx.x)	(xx.x, xx.x)	(xx.x, xx.x)
95% CONFIDENCE INTERVAL	(xx.x, xx.x)	(xx.x, xx.x)	(xx.x, xx.x)	(xx.x, xx.x)
...				
Cumulative Responder Rate by WEEK25 D169				
n (%)	xx (xx.x)	xx (xx.x)	xx (xx.x)	xx (xx.x)

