80% CONFIDENCE INTERVAL	(xx.x, xx.x)	(xx.x, xx.x)	(xx.x, xx.x)	(xx.x, xx.x)
95% CONFIDENCE INTERVAL	(xx.x, xx.x)	(xx.x, xx.x)	(xx.x, xx.x)	(xx.x, xx.x)

Note: Patients are classified into different dose levels according to the maximum dose they received during the 12 week treatment period.
 Control of disease activity (CDA) is defined as the time at which new lesions cease to form and established lesions begin to heal. Cumulative responder rate is used, i.e., any patient achieves the response at any study visit is counted into all the later study visits.
 Unscheduled visits are not included in this summary.
 Patients who ever achieved CDA and had daily prednis(ol)one >0.5 mg/kg before a specific visit during the study treatment will be counted as responders.
 Two-sided 80% and 95% confidence intervals are calculated using the Exact (Clopper-Pearson) method. Percentages are based on the number of patients in the respective dose levels in the Analysis Population.

Source Data: Listing 16.2.4.1.5

<DIRECTORY PATH>PROGRAM NAME Executed: DDMMYYYY hh:mm

Repeat table for following populations

Table 14.2.2.4.6.2

Cumulative Incidence of Patients who Achieved Control of Disease Activity (CDA) with Prednis(ol)one >0.5
mg/kg by Visit
mITT Population

Table 14.2.2.4.6.3

Cumulative Incidence of Patients who Achieved Control of Disease Activity (CDA) with Prednis(ol)one >0.5
mg/kg by Visit
Per Protocol Population

Table 14.2.2.5.1.1
 Proportion of Patients who Achieved Complete Response (CR) at Visit
 ITT Population

Visit	400 mg (N=xx)	500 mg (N=xx)	600 mg (N=xx)	Total (N=xx)
WEEK3 D15				
n (%)	xx (xx.x)	xx (xx.x)	xx (xx.x)	xx (xx.x)
80% CONFIDENCE INTERVAL	(xx.x, xx.x)	(xx.x, xx.x)	(xx.x, xx.x)	(xx.x, xx.x)
95% CONFIDENCE INTERVAL	(xx.x, xx.x)	(xx.x, xx.x)	(xx.x, xx.x)	(xx.x, xx.x)
WEEK5 D29				
n (%)	xx (xx.x)	xx (xx.x)	xx (xx.x)	xx (xx.x)
80% CONFIDENCE INTERVAL	(xx.x, xx.x)	(xx.x, xx.x)	(xx.x, xx.x)	(xx.x, xx.x)
95% CONFIDENCE INTERVAL	(xx.x, xx.x)	(xx.x, xx.x)	(xx.x, xx.x)	(xx.x, xx.x)
...				
WEEK25 D169				
n (%)	xx (xx.x)	xx (xx.x)	xx (xx.x)	xx (xx.x)
80% CONFIDENCE INTERVAL	(xx.x, xx.x)	(xx.x, xx.x)	(xx.x, xx.x)	(xx.x, xx.x)
95% CONFIDENCE INTERVAL	(xx.x, xx.x)	(xx.x, xx.x)	(xx.x, xx.x)	(xx.x, xx.x)

Note: Patients are classified into different dose levels according to the maximum dose they received during the 12 week treatment period.

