<DIRECTORY PATH>PROGRAM NAME Executed: DMMMMYYYY hh:mm

Prog Note: For all efficacy and safety by visit summaries, add "unscheduled" visit after other visits if such data exist in the database.

Repeat for the following populations

Table 14.2.2.5.2.2

Proportion of Patients who Achieved Complete Response (CR) without Prednis(ol)one >0.5 mg/kg at Visit
mITT Population

Table 14.2.2.5.2.3

Proportion of Patients who Achieved Complete Response (CR) without Prednis(ol)one >0.5 mg/kg at Visit
Per Protocol Population

Table 14.2.2.5.3.1
 Proportion of Patients who Achieved Complete Response (CR) with Prednis(ol)one >0.5 mg/kg at Visit
 ITT Population

Visit	400 mg (N=xx)	500 mg (N=xx)	600 mg (N=xx)	Total (N=xx)
WEEK3 D15				
n (%)	xx (xx.x)	xx (xx.x)	xx (xx.x)	xx (xx.x)
80% CONFIDENCE INTERVAL	(xx.x, xx.x)	(xx.x, xx.x)	(xx.x, xx.x)	(xx.x, xx.x)
95% CONFIDENCE INTERVAL	(xx.x, xx.x)	(xx.x, xx.x)	(xx.x, xx.x)	(xx.x, xx.x)
WEEK5 D29				
n (%)	xx (xx.x)	xx (xx.x)	xx (xx.x)	xx (xx.x)
80% CONFIDENCE INTERVAL	(xx.x, xx.x)	(xx.x, xx.x)	(xx.x, xx.x)	(xx.x, xx.x)
95% CONFIDENCE INTERVAL	(xx.x, xx.x)	(xx.x, xx.x)	(xx.x, xx.x)	(xx.x, xx.x)
...				
WEEK25 D169				
n (%)	xx (xx.x)	xx (xx.x)	xx (xx.x)	xx (xx.x)
80% CONFIDENCE INTERVAL	(xx.x, xx.x)	(xx.x, xx.x)	(xx.x, xx.x)	(xx.x, xx.x)
95% CONFIDENCE INTERVAL	(xx.x, xx.x)	(xx.x, xx.x)	(xx.x, xx.x)	(xx.x, xx.x)

Note: Patients are classified into different dose levels according to the maximum dose they received during the 12 week treatment period.
 Complete response (CR) is defined as the absence of new or established lesions while the patient is receiving minimal or no non-PRN 1008 immunotherapy.
 Patients who achieved CR at a specific visit and had daily prednis(ol)one >0.5 mg/kg on or before the first CR date during the study treatment will be counted as responders.
 Two-sided 80% and 95% confidence intervals are calculated using the Exact (Clopper-Pearson) method.
 Percentages are based on the number of patients in the respective dose levels in the Analysis Population.
 Only Systemetic Corticosteroids are considered for this table.
 Source Data: Listing 16.2.4.1.5

<DIRECTORY PATH>PROGRAM NAME Executed: DMMMMYYYY hh:mm
 Prog Note: For all efficacy and safety by visit summaries, add "unscheduled" visit after other visits if such data exist in the database.
 Repeat for the following populations

Table 14.2.2.5.3.2

Proportion of Patients who Achieved Complete Response (CR) with Prednis(ol)one >0.5 mg/kg at Visit

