Table B.14.2.2.12.1 Proportion of patients Achieved CR with prednis(ol)one >0.5 mg/kg by Visit (mITT Population)

Table B.14.2.2.12.2 Proportion of patients Achieved CR with prednis(ol)one >0.5 mg/kg by Visit (Completer Population)

Table B.14.2.2.12.3 Proportion of patients Achieved CR with prednis(ol)one >0.5 mg/kg by Visit (PP Population)

Table B.14.2.2.13.1 Proportion of patients Achieved CR without prednis(ol)one >0.5 mg/kg by Visit (mITT Population)

Table B.14.2.2.13.2 Proportion of patients Achieved CR without prednis(ol)one >0.5 mg/kg by Visit (Completer Population)

Table B.14.2.2.13.3 Proportion of patients Achieved CR without prednis(ol)one >0.5 mg/kg by Visit (PP Population)

Table B.14.2.2.14.1 Proportion of patients Achieved CR at or Prior to Week 25 with prednis(ol)one >0.5 mg/kg (mITT Population)

Achieved CDA at or Prior to Week 5 without prednis(ol)one >0.5 mg/kg	400 mg QD (N = n)	400 mg BID (N = n)	600 mg BID (N = n)	Overall (N = n)
N achieved (%)	x (x.x)	x (x.x)	x (x.x)	x (x.x)
- 80% CI	x.xx, x.xx	x.xx, x.xx	x.xx, x.xx	x.xx, x.xx
- 95% CI	x.xx, x.xx	x.xx, x.xx	x.xx, x.xx	x.xx, x.xx

Percentages are based on the number of patients in each dose group and overall.

Patients are classified into different dose levels according to the dose they received prior to achieving CR.

Confidence Intervals are based on the Exact (Clopper-Pearson) method.

Primary efficacy endpoint: Proportion of patients who achieved CR within 24 weeks of starting PRN1008 treatment, i.e. At or prior to Week 5, without prednis(ol)one equivalent > 0.5 mg/kg on the day prior to the assessment.

Program: <program name (date, time)>, Path: <path>

Table B.14.2.2.14.2 Proportion of patients Achieved CR at or Prior to Week 25 with prednis(ol)one >0.5 mg/kg (Completer Population)

Table B.14.2.2.14.3 Proportion of patients Achieved CR at or Prior to Week 25 with prednis(ol)one >0.5 mg/kg (PP Population)

Table B.14.2.2.15.1 Proportion of patients Achieved CR at or Prior to Week 25 without prednis(ol)one >0.5 mg/kg (mITT Population)

Table B.14.2.2.15.2 Proportion of patients Achieved CR at or Prior to Week 25 without prednis(ol)one >0.5 mg/kg (Completer Population)

Table B.14.2.2.15.3 Proportion of patients Achieved CR at or Prior to Week 25 without prednis(ol)one >0.5 mg/kg (PP Population)

Table B.14.2.2.16.1 Duration of Complete Remission (CR) (mITT Population)

	400 mg QD (N = n)	400 mg BID (N = n)	600 mg BID (N = n)	Overall (N = n)
Duration of CR	x	x	x	x

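### In the Part A SAP, the at-visit CDA table for responses with high-dose steroid carries the rule for responses without it, and the cumulative with and without tables use different steroid cut-offs

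*SAP*

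**What the plan says.** Section 3.2.3 of the Part A SAP lists, as secondary endpoints, CDA and CR at each visit and by each visit, split by whether more than 0.5 mg/kg prednis(ol)one was needed. Section 13 records that the by-visit and cumulative summaries were added to the protocol's list.

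**At-visit CDA.** Table 14.2.2.4.3.1 is titled "Proportion of Patients who Achieved Control of Disease Activity (CDA) with Prednis(ol)one >0.5 mg/kg at Visit". Its footnote counts "Patients who achieved CDA at a specific visit and had no occurrence of daily prednis(ol)one >0.5 mg/kg before each visit date". Table 14.2.2.4.2.1, the *without* table, has the same footnote word for word. Both shells are repeated for the mITT and per-protocol populations.

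**Cumulative CDA.** The *without* shell (14.2.2.4.5.1) counts "Patients who ever achieved CDA and had no occurrence of daily prednis(ol)one >0.5 mg/kg before the first CDA date". The *with* shell (14.2.2.4.6.1) counts "Patients who ever achieved CDA and had daily prednis(ol)one >0.5 mg/kg before a specific visit during the study treatment". The cumulative CR shells (14.2.2.5.5.1 and 14.2.2.5.6.1) differ in the same way. All four state that a patient who has responded at one visit stays in the count at every later visit.

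**Body text.** Sections 8.2.4 and 8.2.5 describe only the *without* summary. For it they use "CS doses from Day 1 to the day before the date of the visit". Neither section defines the *with* rule, so nothing in the text overrides the footnotes.

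**Part B.** Table B.14.2.2.14.1 is titled for CR by Week 25 with more than 0.5 mg/kg, but its row label reads "Achieved CDA at or Prior to Week 5 without prednis(ol)one >0.5 mg/kg".

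**The concern.** These tables exist to separate responses reached on PRN1008 with no more than low-dose steroid from responses that also needed high-dose steroid. For that, each responder should fall in exactly one half, and the halves should add up to the parent table of all responders. A programmer who follows the at-visit CDA footnote produces two copies of the *without* table and no count of high-dose responses. One who follows the cumulative footnotes places some patients in both halves. A reader could then misjudge how often response depended on high-dose steroid, and these results are meant to inform the design of later trials.

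**Working it through.** The plan states no figure on this point, so the check compares the rules and then bounds the effect.

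**1. At-visit CDA.** The two footnotes are identical, so at every visit the *with* count equals the *without* count. A CDA patient with no prior high dose is in both tables. A CDA patient with a prior high dose is in neither. The at-visit CR table (14.2.2.5.3.1) has the right direction: "Patients who achieved CR at a specific visit and had daily prednis(ol)one >0.5 mg/kg on or before the first CR date". The CDA footnote is therefore a slip in one shell and not a convention of the plan.

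**2. Cumulative CDA.** Four patient patterns, classified by the printed footnotes at the Day 15, 29, 57 and 85 visits:

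| Pattern | Counted *without* | Counted *with* | Times counted |
|---|---|---|---|
| First CDA Day 29, never high dose | from Day 29 | never | 1 |
| High dose Day 20, first CDA Day 29 | never | from Day 29 | 1 |
| First CDA Day 15, high dose Day 40 | from Day 15 | from Day 57 | 2 from Day 57 |
| High dose Day 20, no CDA | never | never | 0 |

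Only the third pattern is counted twice. The plan foresees it: Section 8.1 keeps such a patient as a primary responder. The CR shells behave in the same way.

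**3. Which single cut-off works.**
- *Dose before the first response, in both halves.* The third patient is *without* throughout and never *with*. The halves do not overlap, and carrying responders forward causes no conflict.
- *Dose up to the visit, in both halves, with carry-forward.* The third patient enters *without* at Day 15 and is carried forward, then enters *with* at Day 57. The double count remains.
- *Dose up to the visit, without carry-forward.* The overlap disappears, but the patient leaves the *without* count at Day 57, which contradicts the shells' carry-forward rule.

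**4. Size on the interim counts.** Inputs from protocol Section 1.4.2.1: 21 patients dosed, 18 with efficacy data, 11 with CDA on low-dose steroid by the Week 5 visit, and 2 who needed high-dose steroid for a time. I take high-dose to mean above 0.5 mg/kg and assume that both patients belong to the 18.
- At-visit *with* table at Week 5, as printed: anyone in CDA with no prior high dose also meets the primary endpoint, so at most 11/18 = 61.1% (exact 80% CI 43.3 to 76.9).
- The same table with the rule corrected: at most 2/18 = 11.1% (exact 80% CI 3.0 to 26.9).
- Cumulative overlap as printed: 0 to 2 patients, or 0 to 2/18 = 11.1 percentage points. With all 21 dosed patients as the denominator, which is the ITT definition, the upper end is 2/21 = 9.5 points.

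These are bounds. The protocol does not say whether the two patients reached CDA before or after the high dose, or whether the 11 were still in CDA at the Week 5 visit.

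**The case against.** The strongest reply is that this is an obvious copying slip in one shell. The title, the endpoint list in Section 3.2.3 and Section 13 show the intent, and source Listing 16.2.4.1.5 carries a per-visit flag for doses above 0.5 mg/kg, so a careful programmer would probably get it right. That stands as a reason to treat this as a specification error. It does not remove the error, because the footnote is the only stated rule for that table.

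A second reply is that the SAP nowhere says the two halves must add up to the parent table, and that Section 8.2.5 could serve as the common cut-off. Adding up is indeed not a stated requirement. But one patient in both halves defeats the purpose of the split, and the Section 8.2.5 cut-off combined with carry-forward still double counts.

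A reader might infer that the SAP has three competing windows and that a cumulative count could fall over time. The documents do not support this. The Section 8.2.5 window is essentially that of the *with* shells, differing at most at off-treatment visits. The shells' carry-forward rule prevents a fall, which could arise only if Section 8.2.5 were read apart from its shells.

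A reader might also infer that Part B repeats the fault in full. Its footnote is garbled: it refers to CR within 24 weeks, then to Week 5 and to no high dose. But items 14 and 15 in Sections 4.3 and 5.4.2.1 of the Part B SAP are correct, and Section 6 allows the shells to be adjusted.

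**Conclusion.** The point holds as an error of specification in secondary summaries of the Part A SAP, and it should be corrected. The reversed rule is confined to the at-visit CDA *with* shell in its three populations. The other *with* shells for CDA and CR do require high-dose use. Double counting in the cumulative tables is confined to patients whose first high dose comes after the first CDA or CR: 0 to 2 patients on the interim counts, with zero a real possibility.

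It would be tempting to conclude that the reported high-dose responses are wrong and that patients have been counted twice. The documents contain no output and do not show how the tables were programmed, so they support only the conditional statement: the tables are wrong if programmed to the footnotes. The primary endpoint has its own rule in Section 8.1, and the Week 5 and Week 13 responder endpoints have theirs in Sections 8.2.1 to 8.2.3. None of these is affected.

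**What to change.** 1. In Tables 14.2.2.4.3.1 to .3, change the rule to at least one daily prednis(ol)one dose above 0.5 mg/kg from Day 1 to the day before the visit, matching Section 8.2.4. State the same window in 14.2.2.4.2.1 to .3.
2. In the cumulative CDA shells (14.2.2.4.5.x and 14.2.2.4.6.x), the cumulative CR shells (14.2.2.5.5.x and 14.2.2.5.6.x) and Section 8.2.5, classify each patient once, by dose before the first CDA or CR. This fits the carry-forward rule and the primary endpoint as defined in Section 8.1. It also keeps the subgroup tables in line with that endpoint, since they are built by repeating Table 14.2.2.4.5.
3. Add a programmed check that *with* plus *without* equals the parent table at every visit (14.2.2.4.1.x and 14.2.2.4.4.x for CDA, 14.2.2.5.1.x and 14.2.2.5.4.x for CR).
4. Check any existing Part A output against these rules. The Part B SAP reports that the last Part A patient completed on 20 June 2019.
5. As a minor correction, make the row label and footnote of Table B.14.2.2.14.1 match its title and items 14 and 15: CR on or before Week 25, with more than 0.5 mg/kg for the .14 tables and without for the .15 tables.

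The cost is wording in the SAP and shells plus one check. Tables need rerunning only if they were programmed to the footnotes. No new data are needed.
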